8.7. Data analysis

The detailed methodology for data analysis will be described in the Statistical Analysis Plan (SAP).

As a first step, extracted patients will be divided into two cohorts, primary prevention cohort and secondary prevention cohort based on the previous diagnosis of stroke. Clinical and demographic characteristics will be compared with two cohorts at baseline and on the index date (date of the initiation of warfarin and apixaban) and incidence rates of stroke/SE and major bleeding per 1,000 person-years will be calculated during follow-up period. In addition, interaction analysis will be conducted to investigate an interaction between OAC (warfarin/apixaban) and presence or absence of the previous episode of stroke.

- As a second step, only secondary prevention cohort will be used for further analyses as follows, Crude (before IPTW) patient characteristics are compared between warfarin and apixaban cohorts using appropriate methods (continuous variables: unpaired t-test or Mann-Whitney U-test, categorical variables: chi-square test)
- A propensity score is calculated based on multinomial logistic regressions in order to account for confounding effects and to ensure that patient characteristics are balanced between the warfarin cohort and apixaban cohort. An inverse probability of treatment weighting (IPTW) method using the calculated propensity score will be applied. To avoid sample size inflation and to ensure appropriate estimation of variances, s-IPTW (stabilized IPTW) is used here.
- Balanced (after IPTW) patient clinical and demographic characteristics are shown. Covariate balance between apixaban and warfarin cohorts after s-IPTW is assessed in terms of the standardized differences with a threshold of 0.1
- Kaplan Meier curves of balanced cohorts for each endpoint are drawn.
- Incidence rates of endpoints are calculated and shown per 1000 person-years.
- Hazard ratios with 95% confidence intervals will be calculated using a Cox proportional hazards regression model that incorporate only the index OACs as independent variables.

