### 4. ANALYSIS SETS/POPULATIONS

#### 4.1. FULL ANALYSIS SET

##### 4.1.1. Inclusion criteria

*Patients must meet all the following selection criteria*

1. *Patients registered in the MDV database 2008 through 2021.*
2. *Patients newly diagnosed with non-valvular atrial fibrillation*
3. *Patients who started anticoagulation treatment with either warfarin or apixaban after diagnosis of NVAF*
4. *Age 20 years or older on the index date*
5. *Patients who have a history\* of stroke (cerebral infarction, cardioembolic stroke, or hemorrhagic stroke) or TIA before the index date are inclusion criteria only for secondary prevention cohort, otherwise patients will be included in the primary prevention cohort.*

\* A history of stroke is checked as far back as possible from the INDEX DATE to see if there is a history of stroke. That is, the period is from the date each patient first appeared in the MDV database to the day before the index date.

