#### 7.1.2. Patient characteristic balancing

[figure not shown]
In this study, matched cohorts (warfarin cohort versus apixaban cohort) will be created. A propensity score will be calculated based on multivariable logistic regressions in order to account for confounding effects\* and to ensure that patient characteristics will be balanced between the warfarin cohort and apixaban cohort. An inverse probability of treatment weighting (IPTW) method using the calculated propensity score will be applied. To avoid sample size inflation and to ensure appropriate estimation of variances, s-IPTW (stabilized IPTW) is used here.

Balanced (after IPTW) patient clinical and demographic characteristics will be shown. Covariate balance between apixaban and warfarin cohorts after s-IPTW will be assessed in terms of the standardized differences with a threshold of 0.1. We will present the data for each variables and standardized differences in the same table side by side to ensure that two cohorts are balanced after IPTW.

\* Covariates used for the calculation of propensity score

- Gender: male or female
- Age: absolute years
- BMI: categories BMI (kg/m^2) (<18, 18 to <22, 22 to <25, 25+, missing)
- CHADS2 score: absolute score, categories (0, 1, 2, 3, 4, 5, 6)

PFIZER CONFIDENTIAL

[figure not shown]

- CHA2DS2-VASc: absolute score, categories (0, 1, 2, 3, 4, 5, 6, 7, 8, 9)
- Treatment status of the most recent stroke before the index date (outpatient treatment, inpatient treatment, missing)
- mRS (modified Rankin Scale) at time of admission due to most recent stroke (0,1,2,3,4,5, missing)
- JCS (Japan coma scale) at time of admission due to most recent stroke (I, II, III, missing)
- ADL (Activities of daily living) at time of admission due to most recent stroke (0-19, 20-39, 40-59, 60-79, 80-100, missing)
- Duration of hospitalization due to most recent stroke
- Destination after discharge from hospitalization due to most recent stroke (1 or 5 or other (2,3,4,6,7,8,9))
- Use of tPA or urokinase for treatment of most recent ischemic stroke (thrombolytic therapy)
- Type of most recent stroke stroke (TIA, ischemic stroke, cerebral bleeding, cardiogenic thromboembolism, unknown/others)
- 

*Note: in patients with a medical history of incidence multiple stroke events, only information regarding most recent stroke (i.e., stroke event closest to the index date) will be used.*

- Comorbidities
  - Hypertension
  - Heart failure in baseline

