  - Coronary heart disease in baseline
  - Peripheral arterial disorder in baseline
  - History of myocardial infarction
  - Hyperthyroidism or thyrotoxicosis in baseline
  - Diabetes in baseline
  - Liver diseases in baseline
  - Diabetes mellitus diagnosis in baseline
  - Cancer diagnosis in baseline
  - Dementia in baseline
  - Renal diseases in baseline
  - Gastrointestinal ulcer in baseline

PFIZER CONFIDENTIAL

- History of bleeding
- Medicines
  - Treated with antiplatelet drug in baseline
  - Treated with NSAIDs in baseline
  - Treated with anti-hypertensives in baseline
  - Treated with anti-arrhythmics in baseline
  - Treated with beta-blockers in baseline
  - Treated with heparins in baseline
- Others
  - Cardioversion
  - Cardiac ablation

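### The propensity score describes only the most recent stroke, so the number of prior strokes and the type and severity of earlier ones are neither targeted by the weights nor checked for balance

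*SAP*

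**What the plan says.** The covariate list in SAP 7.1.2 has eight items that describe the qualifying stroke: treatment status, mRS, JCS, ADL, length of stay, discharge destination, thrombolysis and type. They concern the latest event. The disability item, for example, reads "mRS (modified Rankin Scale) at time of admission due to most recent stroke (0,1,2,3,4,5, missing", and the type item has the categories "TIA, ischemic stroke, cerebral bleeding, cardiogenic thromboembolism, unknown/others". A note makes the rule explicit for anyone with more than one recorded stroke: "only information regarding most recent stroke (i.e., stroke event closest to the index date) will be used".

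Four other places bear on the point:

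- The same list has a separate item, "History of bleeding". Unlike most of its neighbors it carries no baseline-window limit, and it is not tied to the latest stroke. Its codes would be in the spreadsheet named in SAP Appendix 3, which the text available to us does not reproduce.
- SAP 4.1.1 searches for stroke history over the whole record: "the period is from the date each patient first appeared in the MDV database to the day before the index date".
- SAP 5.4 lists previous stroke, previous TIA and type of previous stroke as patient characteristics. None is restricted to the latest event.
- Protocol 8.7 specifies a Cox model "that incorporate only the index OACs as independent variables".

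**The concern.** Stroke history defines the secondary prevention cohort, and the plan treats stroke type and severity as confounders by listing eight such items. Yet a patient with several strokes is described by one. Because TIA is a category of the type item, a disabling stroke followed by an outpatient TIA enters as TIA, treated as an outpatient, with mRS, JCS and ADL missing because there was no admission for that event. A patient with three strokes can look the same as a patient with one.

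If the number or nature of earlier strokes influences both the choice of drug and the risk of recurrence or bleeding, the weighted comparison may carry confounding that the available records could have reduced. The planned check on the propensity covariates would not show it.

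**Working it through.** The plan gives no figure on this point, so the first part is a reading of the text.

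**What is covered.** I went through the list in SAP 7.1.2 item by item.

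- Number of prior strokes: no item.
- Severity of an earlier stroke: no item. The mRS and ADL at the latest admission may carry some of it, mixed with the effect of the new event, and only where there was an admission.
- Type of an earlier stroke: no item, except that the bleeding-history item may include a hemorrhagic one.
- Outcome model: by Protocol 8.7 it contains treatment only. The summary table in SAP 7.2.3 refers to section 5.4 in its covariate column. Even if that meant adjustment, 5.4 holds no stroke count, and its previous-stroke types are cardioembolic and infarction, with no hemorrhagic category.

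**Size, by illustration.** Let pA and pW be the share of apixaban and warfarin patients with the omitted factor after weighting, and RR its effect on the outcome. Assume that RR is the same in both arms and that the outcome is rare. Then

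factor on the hazard ratio = [1 + pA(RR − 1)] / [1 + pW(RR − 1)].

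All prevalences and risk ratios below are assumptions; the documents give none. Only the hazard ratio of 0.65 comes from the plan (SAP 7.2.2). The standardized difference is |pA − pW| / √{[pA(1 − pA) + pW(1 − pW)]/2}.

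| Factor, pA / pW | RR | Factor on HR | Arms swapped | Std. difference | HR behind an observed 0.65 (as shown / swapped) |
|---|---|---|---|---|---|
| More than one prior stroke, 22% / 20% | 1.3 | 1.066/1.060 = 1.006 | 0.994 | 0.05 | 0.646 / 0.654 |
| More than one prior stroke, 25% / 20% | 1.6 | 1.150/1.120 = 1.027 | 0.974 | 0.12 | 0.633 / 0.667 |
| More than one prior stroke, 30% / 20% | 2.0 | 1.300/1.200 = 1.083 | 0.923 | 0.23 | 0.600 / 0.704 |
| Earlier hemorrhagic stroke, 5% / 3%, on hemorrhagic outcomes | 3 | 1.100/1.060 = 1.038 | 0.964 | 0.10 | not applied |

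The last column is 0.65 divided by the factor. Equal prevalence gives a factor of exactly 1.

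A harsher case shows how far this depends on the assumptions. With 10% under apixaban, 20% under warfarin and RR 3, the factor is 1.2/1.4 = 0.857, and an observed 0.65 would stand for 0.65/0.857 = 0.76. That needs a standardized difference of 0.28 to remain after weighting.

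The second and third rows, and the harsher case, exceed the SAP's cut-off of 0.1. If these factors were in the balance table, imbalances of that size would be seen.

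**The case against.** A reader might infer that the plan throws away an earlier hemorrhagic stroke and leaves strong drivers of recurrence and bleeding unbalanced. The documents do not support that, for three reasons.

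- The bleeding-history item may capture an earlier hemorrhagic stroke. What remains is that a single item may not separate intracranial from other bleeding.
- Imbalance after weighting is not shown. Age, both stroke-risk scores, dementia, antiplatelet use and the state of the patient at the latest stroke are all in the score, and some of these plausibly track earlier disability.
- The strength of the omitted factors is not quantified anywhere in the documents.

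It is also fair to say that SAP 5.4, with the before-and-after comparison in SAP 7.1.1, could show that a patient had both a previous stroke and a previous TIA. That is descriptive help, but it gives neither a count nor a hemorrhagic type.

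The plan has general safeguards. SAP 7.2.1 provides E-values for both primary analyses. At a hazard ratio of 0.65 the E-value is 1/0.65 + √[(1/0.65)(1/0.65 − 1)] = 1.538 + 0.910 = 2.45, above the risk ratios and prevalence ratios assumed for more than one prior stroke in the table. Protocol 8.9 admits residual confounding. Both address what cannot be measured; they do not replace using what is recorded.

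The best remaining objection concerns the data. Look-back starts at each patient's first appearance in the database, so its length varies, and care elsewhere is probably not seen (Protocol 8.9 says so for follow-up). A stroke count would partly measure look-back length. This stands, and it shapes the fix.

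**Conclusion.** The point holds as a gap in covariate specification. Number of prior strokes, and type and severity of earlier strokes, are outside the propensity score and its balance check, except possibly through the bleeding-history item and, descriptively, the previous stroke and TIA items in SAP 5.4.

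It is not a demonstration of bias. Whether the hazard ratio moves, and which way, depends on whether these factors still differ between arms after weighting, which the documents cannot tell us. Under the tabulated assumptions the factor is about 1.01 to 1.08 in either direction, which is modest. It would exceed that range only under a larger remaining imbalance or a stronger effect. The change is still worth making, because the records are already searched and the remedy is cheap.

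**What to change.** Keep the most-recent-stroke items. Add three items to the propensity score and to the standardized-difference table:

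1. Any prior hemorrhagic stroke over the full look-back, separate from other bleeding history. State which codes the existing bleeding-history item covers.
2. More than one prior distinct stroke admission (yes/no). SAP 5.1.1 already defines recurrence as discharge followed by readmission mainly for stroke, and the same rule can separate admissions before the index date.
3. Any prior inpatient-treated ischemic stroke (yes/no). This adds little for patients with one stroke, but it closes the stroke-then-TIA gap.

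Because look-back length varies, report it by arm or include it as a covariate.

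The cost is a change of SAP wording and a few derived variables, with no new data. The preliminary count of more than 15,000 secondary prevention patients (SAP 7.2.2) should leave room for the extra terms. The downside is that the count remains imperfect where earlier care took place outside the database.

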1. LIST OF ABBREVIATIONS

Abbreviation	Definition
AF	Atrial fibrillation
COPD	Chronic obstructive pulmonary disease
DOAC	Direct oral anticoagulant
HAS-BLED	Not an abbreviation. Hypertension, Abnormal renal / liver function, Stroke, Bleeding, Labile INRs, Elderly, Drugs / alcohol
ICD-10	International classification of diseases-10
ICH	Intracranial hemorrhage
ID	Identifier
IEC	Independent ethics committee
IPTW	Inverse probability of treatment weighting
IRB	Institutional review board
MDV	Medical Data Vision Ltd.
NSAID	Non-steroidal anti-inflammatory drug
NVAF	Non-valvular atrial fibrillation
OAC	Oral anticoagulant
RWE	Real world evidence
SAP	Statistical Analysis Plan
SE	Systemic embolism
TIA	Transient ischemic attack

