8.9. Limitations of the research methods

Our study, like most retrospective analyses using claims data, has several intrinsic limitations and certain expected biases.

1. The data we will use is obtained from a claims database containing information provided by hospitals applying the flat-fee payment system, which are mostly large hospitals responsible for acute care. Therefore, a significant proportion of the patients included in the present analysis will be likely in poorer health than the average population requiring hospitalization, possibly having more comorbidities and higher risk of stroke and bleeding.
2. The claims data we will use here do not include vital signs or laboratory data such as blood pressure, international normalized ratio values, and renal function parameters, which is also why we could not calculate a HAS-BLED score. These variables will not be considered in the calculation of the propensity score, and there is no guarantee that such characteristics are fully balanced after s-IPTW. Therefore, although we will compute a propensity score based on multiple variables that may affect the risk of stroke and bleeding, the influence of unexamined confounding factors will not be fully excluded.
3. We will not provide an estimation of follow-up loss, as we will have no subsequent data on patients who visited a different hospital or clinic after being registered with one of the hospitals contributing to the MDV database. This could result in an underestimation of the incidence of stroke or major bleeding events.

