### 5.4. COVARIATES

Variable	Role	Operational definition
Previous stroke		
Previous incidence of stroke	Patient characteristic:	
Previous incidence of TIA	Patient characteristic:	Defined elsewhere using ICD-10 codes

PFIZER CONFIDENTIAL

Types of previous stroke	Patient characteristic:	cardioembolic stroke or cerebral infarction
Treatment status	Patient characteristic:	Inpatients or outpatients
Hospitalization days	Patient characteristic:	0 or days in hospital
NVAF diagnosis and treatment		
Year	Patient characteristic	Year first diagnosed with NVAF
Anticoagulant	Patient characteristic	Warfarin or apixaban
Patients		
age	Patient characteristics on index date	Years
Age category	Patient characteristics on index date	
age $\leq 65$		
age $65 < , \leq 75$		
age $75 <$		
Gender category	Patient characteristics on index date	Male or female
Body weight	Baseline characteristic	Kg (if available)
Height	Baseline characteristic	cm (if available)
BMI	Baseline characteristic	Calculated from body weight and height using a formula of (weight [kg]) / (height [m]) 
Comorbidity profile		
Chronic obstructive pulmonary disease (COPD)	Baseline characteristic	Defined elsewhere using ICD-10 codes
Congestive heart disease	Baseline characteristic	Defined elsewhere using ICD-10 codes
Ischemic heart/coronary artery disease	Baseline characteristic	Defined elsewhere using ICD-10 codes
Diabetes	Baseline characteristic	Defined elsewhere using ICD-10 codes
Hyperlipidemia	Baseline characteristic	Defined elsewhere using ICD-10 codes
Hypertension	Baseline characteristic	Defined elsewhere using ICD-10 codes
Liver disease	Baseline characteristic	Defined elsewhere using ICD-10 codes
Renal disease	Baseline characteristic	Defined elsewhere using ICD-10 codes
Peripheral vascular disease	Baseline characteristic	Defined elsewhere using ICD-10 codes
Pregnancy	Exclusion criteria	Presence of "pregnancy"-related ICD-10 codes.

PFIZER CONFIDENTIAL

Cancer	Baseline characteristic	Defined elsewhere using ICD-10 codes
VTE	Baseline characteristic (exclusion criteria)	Defined elsewhere using ICD-10 codes
Medicines		
Anti-hypertensive drugs	Baseline characteristic	Defined elsewhere using drug codes
Anti-platelet drugs	Baseline characteristic	Defined elsewhere using drug codes
NSAIDs (chronic use*)	Baseline characteristic	Defined elsewhere using drug codes
Statins	Baseline characteristic	Defined elsewhere using drug codes
Outcomes		

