**9.3. APPENDIX 3: DIAGNOSIS AND PROCEDURE CODES USED IN THE STUDY**

The list of ICD-10 codes is shown in following excel sheet.

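### Kidney disease enters the propensity score as one ungraded item and dialysis is handled nowhere, so an imbalance in renal severity between the drugs would be neither corrected nor visible

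*SAP*

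**What the plan says.** - **Adjustment.** SAP 7.1.2 lists the propensity-score covariates. The only kidney item is "Renal diseases in baseline". BMI, mRS, JCS, ADL and type of stroke carry explicit categories in the same list; the kidney item carries none.
- **Definition.** SAP 5.4 describes renal disease as "Defined elsewhere using ICD-10 codes". SAP Appendix 3 is headed "DIAGNOSIS AND PROCEDURE CODES USED IN THE STUDY", but the sentence below it reads "The list of ICD-10 codes is shown in following excel sheet". The sheet is not part of the text.
- **Dialysis, end-stage disease and CKD stage.** None is named in the exclusions (protocol 8.2.2, SAP 4.1.2), the covariates (SAP 5.4 and 7.1.2), the subgroups (SAP 4.4, none planned) or the sensitivity analysis (SAP 7.2.1, E-values only).
- **Outcome model and balance check.** Protocol 8.7 specifies a Cox model with the index anticoagulant as the only independent variable. SAP 7.1.1 and 7.1.2 judge balance by a standardised difference of 0.1 on the tabulated characteristics.
- **Stated limitation.** Protocol 8.9 says the claims data "do not include vital signs or laboratory data such as blood pressure, international normalized ratio values, and renal function parameters", gives this as the reason HAS-BLED cannot be calculated, and adds that "there is no guarantee that such characteristics are fully balanced after s-IPTW". The protocol's abbreviation list shows "Abnormal renal / liver function" as a HAS-BLED component.

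**The concern.** Weighting is the plan's only protection against confounding in the two primary comparisons. It balances what is in the score. If the renal item is a simple flag, the weighted arms can agree on how many patients have renal disease and still differ in how severe it is. A treatment-only Cox model cannot repair that, and a balance table showing the flag alone would look satisfactory.

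The protocol itself treats renal function as relevant to bleeding risk and admits it may stay unbalanced. Laboratory severity cannot be recovered from these data. Dialysis is the extreme of that severity and may be identifiable from codes, so part of an admitted limitation may be removable. At stake is a shift in either primary hazard ratio that nobody would see, with no count by drug from which to judge it.

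**Working it through.** **The plan's own figures first.** The SAP 7.2.2 table reproduces with Schoenfeld events, D = (1.96 + 0.84)² / (0.25 × ln(HR)²), divided by the sum of the two arms' event probabilities, 1 − exp(−rate × 2 years), with 1:1 arms and no censoring. For HR 0.6 at 1.2 %/year, D is about 120 and the result is 3,166 per group, as stated. The other 11 cells agree within 3% (for example 6,817 stated, about 6,897 computed). The sample-size table is not in question.

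**Bias factor.** The documents give no dialysis prevalence, split by drug or risk, so every input here is an assumption:
- r, share of each weighted arm with the renal flag: 10-20%, equal in both arms (flag perfectly balanced)
- d, dialysis share within that stratum: 10-25% on warfarin, 0-1% on apixaban
- H, hazard ratio of dialysis for major bleeding: 2-3

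Factor on the apixaban/warfarin hazard ratio = [1 + r·d(apixaban)·(H − 1)] / [1 + r·d(warfarin)·(H − 1)]

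- Middle case (r = 0.15, d = 0.01 and 0.20, H = 2.5): 1.00225 / 1.045 = 0.959.
- Smallest (r = 0.10, d = 0.01 and 0.10, H = 2): 1.001 / 1.01 = 0.991.
- Largest (r = 0.20, d = 0 and 0.25, H = 3): 1 / 1.10 = 0.909.
- Equal d in both arms: 1.
- Imbalance reversed: the reciprocals, 1.01 to 1.10.

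A wider set (dialysis in 10-30% of renal patients, 80-100% of them on warfarin, 40% of other renal patients on warfarin, H = 2-3) gives 0.83 to 0.99.

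**Would the balance table show it?** In the middle case the dialysis shares of the whole arms are 0.15 × 0.20 = 3% and 0.15 × 0.01 = 0.15%. The standardised difference is (0.03 − 0.0015) / √[(0.03 × 0.97 + 0.0015 × 0.9985) / 2] = 0.23. That is over twice the SAP's cut-off, while the renal flag itself shows 0.

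**Effect on error.** No bleeding rate is given, so this borrows 1.6 %/year from the SAP 7.2.2 table, with 15,000 patients, full 2-year follow-up and no true effect. Events = 15,000 × (1 − exp(−0.032)) = 472. The chance of a significant result favouring apixaban is Φ(√472 / 2 × |ln factor| − 1.96). It is 2.5% with no bias, about 7% at 0.959 and about 18% at 0.909. Earlier censoring would give fewer events and a smaller inflation.

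**Could this alone produce the planned HR of 0.65?** With no dialysis patients on apixaban and H = 3, dialysis would have to be (1/0.65 − 1) / 2 = 27% of the whole warfarin arm. The largest share in the range above is 0.20 × 0.25 = 5%.

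**Cost of a restricted analysis.** If 10-20% have the flag and 10-30% of those are on dialysis across both drugs, 1-6% of 15,000 patients are removed. Power for stroke/SE at HR 0.65 (1:1, 2 years) goes from 0.958 to 0.947-0.957 at 1.2 %/year, and from 0.989 to 0.985-0.989 at 1.6 %/year.

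**The case against.** A reader might infer that end-stage patients collect in the warfarin arm and that both primary hazard ratios are therefore biased towards apixaban. The documents do not support that. They say nothing about which drug such patients receive or about their outcome risk; the HAS-BLED entry and protocol 8.9 link renal function to risk only in general terms. The range above fixes one direction by assumption, and it concerns bleeding only. A stroke/SE effect would need its own assumed dialysis risk.

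Other points in the plan's favour, and what stands:
- *Yes/no coding is an inference.* Correct. The code sheet is not visible, and other comorbidities are listed in the same bare form. What stands is that no level is stated.
- *Other covariates may absorb some severity.* Diabetes, heart failure, antihypertensives, heparins, ADL and mRS are in the score, whereas the bias formula assumes they absorb nothing. The factor may therefore overstate the bias.
- *Exclusion 3 may already remove some dialysis patients.* It would if heparin counts as an anticoagulant. But heparin is also a propensity covariate, which suggests heparin users stay in. The SAP does not say.
- *The limitation is disclosed and E-values are planned.* Both are true and count for the plan. Neither removes bias nor shows whether it is present.
- *Excluding dialysis patients outright changes the target population.* This stands. It would also put SAP 4.1.2 out of line with protocol 8.2.2 unless both were changed, so exclusion should not be the default.

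**Conclusion.** The gap is real: one kidney item without stated levels, no handling of dialysis anywhere, a treatment-only outcome model, and a balance check that cannot see inside the item. Residual confounding by renal severity is possible for both primary endpoints, and the planned output would not reveal it.

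Direction and size are not established. Under the stated assumptions the major-bleeding hazard ratio moves by a factor of 0.91-0.99, or 0.83-0.99 under the wider set. It does not move if dialysis shares are equal, and it moves the other way if the imbalance is reversed. A shift of this size could matter for a result near the null; it would not by itself explain a hazard ratio of 0.65. This is a worthwhile, cheap improvement, not a flaw that invalidates the comparison.

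**What to change.** 1. **SAP 7.1.2 and Appendix 3:** define dialysis/end-stage disease from diagnosis and procedure codes where the extract has them. Whether it does is not stated and should be checked first.
2. **SAP 7.1.2:** grade the renal covariate by ICD-10 stage where recorded (none, unstaged, stage 3 or less, stage 4-5). Report dialysis by drug, with its standardised difference before and after weighting.
3. **SAP 7.2.1:** prespecify a sensitivity analysis of both primary endpoints that removes dialysis patients from both arms and re-estimates the propensity score. State in advance that if the drugs do not overlap in that stratum, this restricted analysis becomes primary, with protocol 8.2.2 and SAP 4.1.2 aligned.
4. **SAP 4.1.2:** state whether heparin counts as an anticoagulant under exclusion 3, since it is also a covariate.

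The cost is some coding, one extra analysis and slightly fewer patients in it (about 1-6% under the assumptions, with a power loss of about 0.01 or less). The restricted result would not apply to dialysis patients.
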